5 TREATMENT OF SUBJECTS

5.1 Coil System

5.1.1 Pre-implant Patient Care

Procedural planning should be performed in accordance with the IFU. Prior to the first treatment, HRCT for assessment of the degree of emphysematous lung tissue should be used to identify the lung lobes most appropriate for treatment.

5.1.2 Implant Procedure

The Coil is delivered through a standard 2.8 mm Inner Diameter therapeutic bronchoscope. The Coil System is a two-part system that consists of:

- 1) Sterile implants (3 sizes: 100 mm, 125 mm, and 150 mm)
- 2) Sterile, disposable, single-use (single-patient) Delivery System consisting of a Cartridge, a Catheter, a Guidewire and Forceps.

Each Coil implantation procedure must be performed under fluoroscopy in accordance with the IFU. Use of general anesthesia or conscious sedation is at the discretion of the bronchoscopist and anesthesiologist. A complete treatment includes two treatments: the first side (upper or lower lobe Coil implantation) followed by treatment of the contralateral side. Procedures must be staggered (contralateral procedure should be scheduled approximately 2 months after first treatment), such that both lungs are not treated during a single procedure. Lobar targeting for Coil implantation will be based on quantitative CT (QCT) densitometry analysis provided by PneumRx, per the PneumRx QCT Service.

The Treatment is considered complete after the contralateral procedure. The investigator can decide to limit the Treatment to one side if there are contraindications preventing the Treatment of the contralateral side.

Each center's PI, or a primary implanter, will perform all Coil treatments in the study if possible. If necessary, a secondary implanter will be trained as a back-up if primary implanter is unavailable.

5.1.3 Post-implant Management

Prophylactic regimen of medications should be administered according to the IFU and standard of care (SoC).

Per the IFU, a chest X-ray or still fluoroscopy image should be done post-procedure to verify Coil placement and to ensure there is no pneumothorax. A second, confirmatory chest X-ray should be done before discharge a minimum of 4 hours following the first chest X-ray. The second, confirmatory X-ray must be two views, posterior anterior (PA) and Lateral.

The Subject will be counseled on expected side-effects of the Coil procedure, including the potential AEs listed in Section 7.7. The Subject will be instructed to contact the treating physician immediately should any of the potential AEs be experienced. It is particularly important that Subjects be instructed at discharge to contact their implanting physician if they experience symptoms that may be indicative of pneumonia or CAIRS/CAO, to ensure that appropriate treatment is delivered.

Follow-up visits should be conducted per the schedule below. Study specific follow -up visits should take place during exacerbation free periods defined as 30 days with symptoms within normal day to day variability.

Treatment Group Subjects:

Visit	Visit window
Baseline visit	Eligibility, inclusion
Randomization	
First coil treatment	No more than 45 days post baseline visit
Second coil treatment	2 months +/- 4 weeks post first procedure
12-month follow-up	12 months +/- 4 weeks post first procedure
36-month follow-up	36 months +/- 4 weeks post first procedure

Control Group Subjects:

Visit	Visit window
Baseline visit	Eligibility, inclusion
Randomization	
First coil treatment	
Second coil treatment	2 months +/- 4 weeks post first procedure
12-month follow-up	12 months +/- 4 weeks post first procedure
36-month follow-up	36 months +/- 4 weeks post first procedure

5.1.4 Duration of Treatment and Follow up

All Subjects randomized to Treatment will be followed for 36 months post initial treatment. Subjects randomized to Control will be allowed immediate treatment and will be followed for 36 months post initial treatment. If Control Subjects do not crossover to treatment, they will exit the study immediately.

5.1.5 Concomitant Therapies or Interventions

Both Treatment and Control Subjects will be given SoC treatment for subjects with GOLD III or IV emphysema, defined as proven optimal medical care for stable COPD, either as presented in the GOLD guidelines (Global Initiative for Chronic Obstructive Lung Disease: Global strategy for the diagnosis, management, and prevention of chronic obstructive pulmonary disease [Updated 2017])⁷ or per national or local standards.

As recommended by the GOLD guidelines, each Subject will continue maintenance bronchodilator therapy, which will include an inhaled long-acting beta-agonist, inhaled anticholinergic, or both. These drugs may also

be combined with theophylline and/or inhaled corticosteroids at the discretion of the treating physician. The physician will be allowed to adjust the subject's pharmacological regimen as needed during the course of the study to manage variations in the subject's condition (e.g., COPD exacerbations). However, the Subject's medical regimen should be optimized at the pre-Treatment Visit, prior to completing the baseline 6MWT and PFTs. Changes in medications or dosages will be recorded in the eCRF.

Pulmonary rehabilitation and maintenance therapy is recommended by the GOLD guidelines. Subjects may participate in pulmonary rehabilitation and maintenance therapy throughout their participation in the study. Post treatment pulmonary rehabilitation or a regular exercise program is strongly encouraged.

6 MEASUREMENTS AND EVALUATIONS

6.1 Treatment Group Assignment

A total of 120 Subjects were randomized in a 2:1 Treatment to Control ratio (80 Treatment group Subjects, 40 Control group Subjects).

Randomization will occur after ERC review of Subject data entered into the EDC. Site will be notified when randomization can occur after ERC review.

6.2 Pulmonary Function Central Laboratory

A PFT Core lab will provide oversight of PFT tests. This will include training of sites, certification of assessors and review of Baseline and 6 month PFT data to ensure valid measurements meeting the standards defined by ATS/ERS (Miller et al., 2005; Wagner et al., 2005; McIntyre et al., 2005, Miller et al., 2005).

6.3 Central Imaging Review

Quantitative assessment of baseline CT imaging will follow the PneumRx QCT process. Minimum scan criteria should be met as defined by the PneumRx QCT service. Sites will upload or send CD or other digital media of HRCT scan to PneumRx QCT service. PneumRx will provide site with a lung densitometry report that will report on the heterogeneity of emphysema, lobar volumes, and the degree of destruction (%LAA) for each lobe which should be used to determine the lobe of each lung to treat with Coils.

6.4 Time and Event Schedule

The eCRFs will be completed by the PI (or an authorized member of the investigator's staff) at the participating site and entered into the EDC database per the event schedule described below. The PI will attest that all entries in the EDC are accurate.

6.4.1 Baseline Visit

After the Subject provides informed consent, the Subject will be evaluated to ensure they are appropriate candidates for use of the Coil System. Eligibility to enroll in the study is assessed as described in Section 4.2.

The following evaluations will be performed as part of the Baseline visit.

- Informed Consent
- Demographic Information
- Medical history information, including comorbidities, smoking status, previous treatments of emphysema and baseline characteristics, physical activity, rehabilitation status
- Medications
- Pulmonary Function Test (PFT)
- Six Minute Walk Test (6MWT)
- Modified Medical Research Council mMRC dyspnea scale will be completed.
- QoL assessments: SGRQ, CAT, and EQ5D will be completed
- Blood gas, including CoHB for smoking cessation confirmation
- Blood test including cardiac panel with BNP test and other biomarker, if available
- Pregnancy test for females of child-bearing potential prior to radiographic procedures
- Echocardiogram
- Vital signs
- Inspiratory and expiratory HRCT (Note: a HRCT scan (inspiratory and expiratory) performed within 6 months prior to baseline may be used if it was acquired per the PneumRx QCT service protocol.)
- Chest X-Ray.

6.4.2 Procedure/Implant Visit

Enrolled Subjects randomized to the either arm will undergo the Coil Treatment in accordance with the approved (CE Mark) IFU. Procedure visits will include 2 sessions: treatment procedure for one lung, followed by treatment procedure for the contralateral side lung, which should be scheduled approximately 2 months following the initial procedure.

The following evaluations will be performed for each procedure visit:

- Pregnancy test for females of child bearing-potential prior to radiographic procedures
- Treatment date
- Duration of bronchoscopy procedure
- Duration of fluoroscopy
- Duration of hospital stay
- Lung lobe and location treated
- Number and size of implanted Coils
- Procedural SAEs (see Section 7)
- Device malfunctions
- Prophylactic medications (antibiotics, steroids – including dosage and start/stop dates)
- Fluoroscopy image immediately post procedure – should be captured in eCRF
- Chest X-ray (PA and Lateral) before discharge at least 4 hours following the fluoroscopy image

6.4.3 Follow-Up Visits

Follow-up office visits will be conducted at 12, and 36 months post first Endobronchial Coil treatment for both Treatment group subjects and Crossover subjects..

Follow-up visits should be conducted per the schedule below. Study specific follow-up visits should take place during exacerbation free periods defined as 30 days with symptoms within normal day to day variability.

12- and 36-month study follow-up visits will include:

- PFT
- AE review
- Medications
- Inspiratory and expiratory HRCT

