SD	Standard Deviation
T	Temperature
TLC	Total Lung Capacity
Tx	Treatment
UADE	Unanticipated Adverse Device Effect
US	United States
USADE	Unanticipated Serious Adverse Device Effect
VC	Vital Capacity

PROTOCOL SYNOPSIS

Reference	BTG-004517-01-FR
Title:	A Randomized Controlled Study of PneumRx Endobronchial Coil System Versus Standard-of-Care Medical Management in the Treatment of Subjects with Severe Emphysema (ELEVATE)
Sponsor:	Boston Scientific Corporation [name]
Timelines and duration:	Study Duration: All Subjects randomized to Treatment will be followed for 36 months post initial treatment. Subjects randomized to Control will be eligible to crossover and receive treatment as soon as possible. Crossover subjects will then be followed for 36 months post initial treatment. Control subjects who choose not to crossover will exit the study immediately. Expected Enrollment Start: Early 2018 Estimated Study Completion: First half 2023
METHOD	
Design:	Prospective, multicenter, open label, randomized (2:1), controlled study comparing outcomes in subjects treated with the PneumRx Endobronchial Coil System (Coil) to a medically-managed control group. The medically-managed control group will be eligible to crossover after 6 months.
Population:	The population studied included severe emphysema patients indicated for Coil treatment per the approved, CE marked Instructions for Use (IFU), who met the following inclusion criteria and did not meet any of the exclusion criteria. Inclusion Criteria: 
 1. Read, understood and signed the Informed Consent form 2. Meets indications for use per the IFU 3. Bilateral heterogeneous and/or homogeneous emphysema 4. 15% predicted \leq Post bronchodilator Forced Expiratory Volume in 1 second (FEV₁) \leq 45% predicted 5. Post bronchodilator Residual Volume (RV) \geq 200% predicted 6. Post bronchodilator Total Lung Capacity (TLC) $>$100% pred. 7. Post bronchodilator RV/TLC $>$55% 8. Dyspnea related to hyperinflation scored \geq 2 on modified Medical Research Council (mMRC) dyspnea scale despite optimal medical management 9. Receiving optimal drug therapy and medical management according to clinical practice. 10. Performing regular physical activity, at least 2 times per week ¹

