
Visits and Assessments:
	
Baseline Visit:
 
After obtaining Subject consent, the Subject’s eligibility for Treatment was evaluated. Relevant medical history, medications, comorbidities, previous treatments of emphysema, physical activity / rehabilitation status, and baseline characteristics were collected and entered into the Electronic Data Capture (EDC) system. Pulmonary Function Test (PFT), pregnancy test, imaging (HRCT scan inspiratory and expiratory,), exercise testing (6 Minute Walk Test – 6MWT), dyspnea assessment (mMRC), quality of life (QoL) assessment (St Georges Respiratory Questionnaire (SGRQ), COPD Assessment Test (CAT), EuroQoL-5 Dimensions QoL questionnaire (EQ-5D), and blood gases (BG) were collected. Eligibility was reviewed by the ERC, and if deemed eligible, subject was randomized.
 
Procedure Visits:
 
Subjects will undergo the Coil treatment. One lung will be treated per procedure, with procedures separated by approximately 2 months. Lobar targeting will be based on quantitative CT (QCT) densitometry analysis and Coils will be placed in the lobe with the higher LAA as measured in Hounsfield units (HU) at a -950 HU threshold.

Procedure data, chest X-ray data, adverse event data, pregnancy test, and medications will be collected and entered into the EDC system.

Each center’s principal investigator (PI), or one primary implanter, will perform all coil treatments in ELEVATE. If necessary, a secondary implanter will also be trained as a back-up.

Follow-up Visits:

Follow-up visits should be conducted per the schedule below. Study specific follow-up visits should take place during exacerbation free periods defined as 30 days with symptoms within normal day-to-day variability.

12- and 36-month study follow-up visits will include:

- PFT
- AE review
- Medications
- Inspiratory and expiratory HRCT

Definition of visit windows:

Patients should have visits scheduled during exacerbation-free periods, defined as 30 days with symptoms within normal day to day variability.

Treatment/Control Group Subjects:

Visit:	Visit Window:
Baseline	Eligibility, Inclusion
Randomization	
Treatment 1	
Treatment 2	2 months +/- 4 weeks post 1st treatment
12 months post Treatment 1	12 months +/- 4 weeks post 1st treatment
36 months post Treatment 1	36 months +/- 4 weeks post 1st treatment

Device:
	
PneumRx Endobronchial Coil System (Coil)

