3.2 Trial Design

This is a prospective, multicenter, open label, randomized (2:1), controlled study comparing outcomes in subjects treated with the Coil System (Treatment) to a medically-managed control group (Control). Control group patients will be eligible for treatment with Coils (Crossover) 6 months after entry into the study.

The study is anticipated to begin enrollment early 2018. All subjects randomized to Treatment will be followed for 36 months post initial treatment. Subjects randomized to Control will be eligible for crossover as soon as possible. Crossover subjects will then be followed for 36 months post initial treatment. The anticipated last patient visit is expected in first half of 2023. If Control subjects choose not to crossover to treatment, they will exit the study immediately.

The data in this study, including Subject characteristics, outcome measures (e.g., health-related QOL, pulmonary function, exercise capacity), and safety (SAEs and specific respiratory AEs of interest), will be collected via the use of an electronic data capture (EDC) system on electronic Case Report Forms (eCRFs).

No biological samples will be taken other than blood draws taken at screening, and no biological samples will be stored for the study.

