8.3 Analysis Populations and Sub-Groups

Intent to Treat Population (ITT) – All randomized Subjects, regardless of whether or not treatment was attempted.

Per Protocol Population (PP) - All randomized Subjects without major protocol deviations (see Section 10.9).

Safety Population - All randomized Subjects who enter the bronchoscopy suite for the initial Coil procedure.

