8.5 Efficacy Analyses

All effectiveness analyses will be analyzed on the ITT population through the 6-month visit, using descriptive statistics to summarize results separately for treatment and control groups. No comparative inferential statistics will be conducted. In addition, descriptive statistics will summarize percent change in FEV₁ from baseline to 12 and 36 months for all coil treated subjects. Baseline will be defined as the last measurement taken prior to coil treatment.

Descriptive statistics will summarize effectiveness endpoints at 12, 24 and 36 months follow-up.

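### Follow-up is dated only from first coil treatment, so never-treated Treatment-arm subjects in the ITT have no scheduled outcome, and time zero for the 6-month results is undefined in that arm

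*Combined protocol and SAP*

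**What the plan says.** Every dated follow-up visit is counted from the first coil procedure. Section 6.4.3 states: "Follow-up office visits will be conducted at 12, and 36 months post first Endobronchial Coil treatment for both Treatment group subjects and Crossover subjects". The window tables agree: "12 months +/- 4 weeks post first procedure" in Section 5.1.3, for both arms, and "12 months +/- 4 weeks post 1st treatment" in the Synopsis. The Synopsis also says "All Subjects randomized to Treatment will be followed for 36 months post initial treatment", which presumes that all of them are treated.

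The ITT population in Section 8.3 is "All randomized Subjects, regardless of whether or not treatment was attempted". Section 8.5 adds: "All effectiveness analyses will be analyzed on the ITT population through the 6-month visit". Baseline is defined there as the last value before coil treatment. Section 8.3 limits the safety population to randomized subjects who reach the bronchoscopy suite for the first procedure, and Section 8.6 promises 6-month incidence rates for both groups without giving a start date.

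The co-primary endpoints (Section 3.4) run from baseline to 6 months, worded alike for both arms. The only 6-month reference with a stated origin concerns Controls: "Control group patients will be eligible for treatment with Coils (Crossover) 6 months after entry into the study" (Section 3.2). For the Treatment arm, Section 5.1.3 sets the first procedure at "No more than 45 days post baseline visit".

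**The concern.** The ITT definition shows that the plan expects some randomized subjects not to be treated and intends to analyze them. The visit schedule gives those subjects nothing to be analyzed with. A Treatment-arm subject who has an exacerbation, changes their mind or dies while waiting for the procedure never starts the clock that the visits run on.

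If sites follow the text, the Treatment side of the ITT summary turns into a summary of treated subjects, and those who do badly before the first procedure disappear from it. The study is described as comparing outcomes between randomized groups, and its objective is to confirm safety and effectiveness. Side-by-side 6-month summaries lose much of the benefit of randomization if one of them is selected on having been treated. An undefined time zero adds a second problem, because two analysts could place the Treatment arm's 6-month point on different dates and both claim to follow the protocol.

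**Working it through.** **1. The plan's own figure.** 120 × 2/3 = 80 Treatment and 120 × 1/3 = 40 Control; 80 + 40 = 120. This agrees with Section 8.1. No alpha, power, effect size or SD is given and the analysis is descriptive, so there is no power calculation to reproduce.

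**2. Who is covered by which rule.**

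| Subject | ITT (8.3) | Safety population (8.3, 8.6) | Dated follow-up (1, 5.1.3, 6.4.3) | Completion or exit rule (4.3, 5.1.4, 6.4.4) |
|---|---|---|---|---|
| Treatment arm, treated | yes | yes | 12 and 36 months from first treatment | completes at 36 months |
| Treatment arm, never treated | yes | no, unless the suite was entered | none | none |
| Control, crosses over | yes | yes, from the procedure | 12 and 36 months from first treatment | completes at 36 months |
| Control, does not cross over | yes | no | none | leaves at once |

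Only the second row has neither a visit nor a rule. Section 4.4 (withdrawal) covers subjects who ask to leave, are lost, or are withdrawn by the investigator. It does not fit a willing subject who simply was not treated. The baseline definition in Section 8.5 also presupposes a procedure that this subject does not have.

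**3. How many.** The documents give no rate. Assuming 0% to 10% of 80:
- 80 × 0 = 0
- 80 × 0.05 = 4
- 80 × 0.10 = 8, which is 8/120 = 6.7% of the ITT.

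**4. Time zero.** The schedules in the Synopsis and in Sections 1, 5.1.3 and 6.4.3 contain no 6-month visit, although Section 6.2 refers to 6-month lung-function data and Section 8.5 to a 6-month visit. No section gives the Treatment arm's origin. The Control reference is not firm either: Sections 3.2, 4.3 and 5.1.4 also allow crossover without a 6-month wait, and these statements must be reconciled.

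**5. Size of a possible offset (conditional).** Let d be the days from the baseline visit to first treatment (0 to 45) and r the days from baseline to randomization (r ≤ d). Six months = 6 × 365.25/12 = 182.6 days.
- Treatment, if counted from first procedure (assumption): 182.6 + d = 182.6 to 227.6 days after baseline.
- Control, if entry is the baseline visit (assumption): 182.6 days. The gap is d, or 0 to 45 days; 45/182.6 = 24.6%.
- Control, if entry is randomization (Section 6.5.10 equates enrollment with randomization): 182.6 + r days. The gap is d − r, so at most 45 − r.
- Both arms counted from one origin: the gap is 0.

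**The case against.** The sentence quoted from Section 6.4.3 is not itself an error. Sections 8.5 and 8.6 restrict the 12- and 36-month FEV₁ and safety summaries to coil-treated subjects, and a treatment-based clock suits those. That stands, so the ITT conflict bites at 6 months. The one loose end is the line in Section 8.5 on endpoints at 12, 24 and 36 months, which names no population.

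It can also be said that the current schedule has no 6-month visit for anyone, so an untreated subject is no worse placed than a treated one. That is fair as far as it goes. But a 6-month visit added with the same anchor as the others would still leave the untreated without one.

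The analysis is descriptive, so no error rate or power is affected. That stands too, but selection distorts descriptive summaries as well as tests. Section 8.2 defers detail to a separate SAP, which is not in the text available here and might define the origin.

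Three stronger readings are tempting, and the documents do not support them:
- **That the two arms' 6-month periods start at different points.** The endpoint wording is the same for both arms, and the anchor in Section 6.4.3 covers 12 and 36 months only. The Treatment origin is unstated, not stated to differ.
- **That the Treatment interval is 25% longer.** This is a ceiling that needs both assumptions in the working and a first procedure on day 45.
- **That early deaths count in Control but not in Treatment.** For safety, the population read literally also leaves out a Control who dies before crossover. For FEV₁ and SGRQ, a subject who dies before 6 months has no value in either arm under any clock.

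**Conclusion.** The point holds as a gap in the plan, and it should be closed. No visit, completion rule or exit rule covers a Treatment-arm subject who is never treated, although the ITT includes that subject. Those who deteriorate or die between randomization and first procedure therefore drop out of the Treatment-arm summaries. Time zero for the Treatment arm's 6-month co-primary and AE/SAE intervals is undefined.

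The size is modest and uncertain. It is 0 to 8 of 80 subjects under an assumed 0% to 10% never treated, and 0 to 45 days of possible offset under assumptions that the documents neither state nor exclude. The direction of any bias is not established. If the untreated are mainly those who worsened while waiting, leaving them out would flatter the Treatment arm.

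**What to change.** - In Sections 8.5 and 8.6, count the 6-month FEV₁, SGRQ, AE/SAE and vital-status intervals from randomization in both arms, on all randomized subjects.
- In Section 6.4.3 and the schedule, state that Treatment-arm subjects who are not treated are followed to 6 months from randomization. Section 7.2 already permits AE collection by telephone. Add no 12- or 36-month visits for them.
- Randomization is described in the past tense, so some 6-month data may be beyond recovery. In that case, report untreated and missing subjects by arm, with reasons and vital status.
- Report the randomization-to-first-treatment interval in the Treatment arm.
- Keep the treatment-based clock for the 12- and 36-month summaries of coil-treated subjects.

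The cost is protocol and SAP wording and contact with a handful of subjects. The Treatment arm's 6-month results would then include a short pre-procedure period and correspondingly less post-procedure time. The loss is d − r in the notation above, so at most 45 days. The reported randomization-to-treatment interval lets readers judge this.
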